10.2.2. Secondary Endpoint Analyses

Secondary efficacy endpoints will include:

- Time-weighted average change in viral shedding as measured by RT-qPCR in nasopharyngeal swab samples from baseline to Day 15
- Change in SARS-CoV-2 viral shedding as measured by RT-qPCR in nasopharyngeal swab samples from baseline to Day 15
- Time to negative RT-qPCR in all tested samples with no subsequent positive RT-qPCR in any tested samples
- Proportion of patients requiring hospitalization due to worsened COVID-19
- Time to resolution of all COVID-19-related symptoms
- All-cause mortality rate at Day 29

The time-weighted average change in viral shedding as measured by RT-qPCR in nasopharyngeal swab samples from baseline to Day 15 is defined as:

$$\frac{\sum_{i=a}^{b-1} [0.5 \times (Y_i + Y_{i+1}) \times (t_{i+1} - t_i)]}{t_b - t_a}$$

where Y_i is the change from baseline in viral shedding at Visit i , t is the time at the specified timepoint (the actual study day), a is the baseline assessment at Day 1, and b is the last assessment at or prior to Day 15 visit. Analysis of covariance (ANCOVA) model with corresponding baseline viral shedding, disease severity, and treatment as covariates will be used. Comparisons of active doses to placebo (90% CIs and p-values) will be provided.

The same MMRM analysis for primary endpoint will be used to analyze the change in SARS-CoV-2 viral shedding from baseline to Day 15. Comparisons of active doses to placebo (90% CIs and p-values) will be provided.

[figure not shown]
[figure not shown]
Kaplan-Meier method will be used to assess the time to negative RT-qPCR. The corresponding quartiles (including the median) will be reported and a two-sided 95% CI of median, if estimable, will be constructed with a generalized Brookmeyer and Crowley method for each dosing group. Patients who have died prior to experiencing the event of interest will be censored on the day of data cutoff.

The number of patients who require hospitalization due to worsened COVID-19 will be counted. Corresponding proportion will be derived and a two-sided binomial exact 95% CI of proportion will be constructed.

Kaplan-Meier method will be used to assess the time to resolution of all COVID-19-related symptoms. The corresponding quartiles (including the median) will be reported and a two-sided 95% CI of median, if estimable, will be constructed with a generalized Brookmeyer and Crowley method for each dosing group. Patients who have died prior to experiencing the event of interest will be censored. Their follow-up length will be arbitrarily set as (data cutoff date – first-patient-in date). This approach is to count death as the worst possible outcome without possibility of recovery.

Kaplan-Meier method will be used to assess all-cause mortalities and corresponding quartiles (including the median) will be reported. A two-sided 95% CI of median, if estimable, will be constructed with a generalized Brookmeyer and Crowley method. Patients who does not die will be censored on the last known date alive.

10.2.3. Exploratory Endpoint Analyses

Safety will be determined by monitoring AEs and laboratory values (hematology, clinical chemistry, coagulation, and urinalysis). Vital signs, physical examinations, and ECG findings will also be used in determining the safety profile. The severity of AEs will be graded according to NCI-CTCAE Version 5.0. The incidence of TEAEs will be reported as the number (percentage) of patients with TEAEs by Medical Dictionary for Regulatory Activities (MedDRA) system organ class and preferred term. Descriptive summary statistics (eg, n, mean, standard deviation, median, minimum, and maximum for continuous variables; n [%] for categorical variables) and changes from baseline will be determined for laboratory parameters and vital signs.

Safety data will be summarized using the Safety Analysis Set.

10.3.1. Extent of Exposure

Extent of exposure to each study drug will be summarized descriptively for the total dose received per patient (mg) and relative dose intensity.

The number (percentage) of patients requiring treatment interruption because of AEs will be summarized for each study drug. Reasons for dose interruption will be summarized as well.

Patient data listings will be provided for all dosing records and for calculated summary statistics.

10.3.2. Adverse Events

The AE verbatim descriptions (investigator's description from the eCRF) will be coded using MedDRA. AEs will be coded to MedDRA lowest level term, preferred term, and primary system organ class.

A TEAE is defined as an AE that had an onset date or a worsening in severity from baseline (pretreatment) on or after the administration of study drug and up to the 30 days after dosing.

The incidence of TEAEs will be reported as the number (percentage) of patients with TEAEs by system organ class and preferred term. A patient will be counted only once by the highest severity grade per NCI-CTCAE Version 5.0 within a system organ class and preferred term, even if the patient experienced more than 1 TEAE within a specific system organ class and preferred term. The number (percentage) of patients with TEAEs will also be summarized by relationship to the study drug.

Treatment-related TEAEs include those events considered by the investigator to be related to study treatment or with missing assessment of the causal relationship. SAEs, deaths, \geq Grade 3 TEAEs, treatment-related TEAEs, and TEAEs that led to treatment discontinuation or treatment interruption will be summarized.

10.3.3. Laboratory Analyses

Clinical laboratory (eg, hematology, clinical chemistry, coagulation, and urinalysis) values will be evaluated for each laboratory parameter as appropriate. Abnormal laboratory values will be flagged and identified as those outside (above or below) the normal range. Reference (normal) ranges for laboratory parameters will be provided. Descriptive summary statistics (eg, n, mean, standard deviation, median, minimum, and maximum for continuous variables; n [%] for categorical variables) for laboratory parameters and their changes from baseline will be calculated. Laboratory values will be summarized by visit and by visit with the maximum postbaseline change.

Laboratory parameters that are graded by NCI-CTCAE Version 5.0 or higher will be summarized by NCI-CTCAE grade. In the summary of laboratory parameters by NCI-CTCAE grade, parameters with NCI-CTCAE grading in both high and low directions will be summarized separately.

10.3.4. Vital Signs

Descriptive statistics for vital sign parameters (systolic and diastolic blood pressure, pulse rate, and body temperature) and changes from baseline will be presented by visit for all visits. Vital signs will be listed by patient and visit.

10.4. Pharmacokinetic Analyses

The PK analyses will include patients with sufficient data to enable estimation of key parameters, such as C_{max} , t_{max} , $t_{1/2}$, AUC_t , AUC_{inf} , AUC_{0-29} , CL, and V_z (as appropriate for data collected), with patients grouped according to treatment received. Non-compartmental or model-based methods will be used as appropriate.

Individual and mean serum BGB-DXP593 concentration versus time data will be tabulated and plotted by dose level. The PK parameters of BGB-DXP593 may be derived and summarized with descriptive statistics (sample size, mean, standard deviation, coefficient of variance, median, minimum, maximum, geometric mean, geometric coefficient of variance). Other PK parameters may be calculated if supported by the data. Individual serum concentration versus time data will be tabulated and plotted by dose level.

Additional PK analyses (such as modeling and simulation using nonlinear mixed effects modelling) may be conducted as appropriate.

10.5. Immunogenicity Analyses

The immunogenicity results will be summarized using descriptive statistics by the number and percentage of patients who develop detectable ADAs. The incidence of positive ADAs and neutralizing ADAs will be reported for evaluable patients. The effect of immunogenicity on PK and safety may be evaluated if data allow.

10.6. Other Exploratory Analyses

10.7. Sample Size Consideration

The sample size calculation is based on the following assumptions:

- The primary endpoint “change from baseline to Day 8 in SARS-CoV-2 viral shedding” is normally distributed
- One-sided significance level $\alpha = 5\%$
- True maximum treatment effect size of BGB-DXP593 versus placebo is $-1.5 \log_{10}$ copies per mL
- Standard deviation is $3.2 \log_{10}$ copies per mL (Wang et al 2020)
- Prespecified candidate models listed in Section 10.2.1

Forty-one patients are needed with primary endpoint data per arm to provide at least 82% power to detect non-flat dose-response relationship. MCPMod approach is used. In order to ensure 41 patients per arm with primary endpoint data, at least 43 patients per arm need to be randomized.

The calculation has been performed using R software, version 3.6.1.

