The immunogenicity results will be summarized using descriptive statistics by the number and percentage of patients who develop detectable ADAs. The incidence of positive and neutralizing ADAs will be reported for evaluable patients. The effect of immunogenicity on PK and safety may be evaluated if data allow.

Sample Size Calculation

Forty-one patients are needed with primary endpoint data per arm to provide at least 82% power to detect non-flat dose-response relationship at one-sided significance level $\alpha = 5\%$. MCPMod approach is used. In order to ensure 41 patients per arm with primary endpoint data, at least 43 patients per arm need to be randomized.

The calculation has been performed using R software, version 3.6.1.

LIST OF ABBREVIATIONS AND TERMS

Abbreviation	Definition
ACE2	angiotensin-converting enzyme 2
ADA	antidrug antibody
AE	adverse event
AUC	area under the concentration-time curve
AUC _{inf}	AUC from time zero to infinity
AUC _t	AUC from time zero to the time of the last quantifiable concentration
AUC ₀₋₂₉	AUC from time zero to Day 29
CI	confidence interval
CL	clearance
C _{max}	maximum observed concentration
COVID-19	coronavirus disease 2019
ECG	electrocardiogram
eCRF	electronic case report form
EDC	electronic data capture (system)
GCP	Good Clinical Practice
IC ₅₀	concentration for inhibition of 50% maximal activity
IC ₉₉	concentration for inhibition of 99% maximal activity
ICF	informed consent form
IDMC	Independent Data Monitoring Committee
IEC	Independent Ethics Committee
IRB	Institutional Review Board
IRT	Interactive Response Technology
mAb	monoclonal antibody
MCPMod	multiple comparison procedures and modelling approaches
MedDRA	Medical Dictionary for Regulatory Activities
NCI-CTCAE	National Cancer Institute-Common Terminology Criteria for Adverse Events
PK	pharmacokinetic(s)
RBD	receptor binding domain
RT-PCR	reverse transcription-polymerase chain reaction
RT-qPCR	reverse transcription-quantitative polymerase chain reaction
SAE	serious adverse event
SARS-CoV-2	Severe Acute Respiratory Syndrome Coronavirus 2
TEAE	treatment-emergent adverse event

Abbreviation	Definition
t_{\max}	time to maximum observed concentration
$t_{1/2}$	terminal half-life
V_z	volume of distribution

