2.2.3. Exploratory Endpoints

3. STUDY DESIGN

3.1. Summary of Study Design

This is a Phase 2, randomized, double-blind, placebo-controlled study to evaluate the efficacy and safety of BGB-DXP593 in patients with mild to moderate COVID-19.

[figure not shown]
The study will be conducted across approximately 20 to 30 sites internationally.

After providing written informed consent, completing all screening assessments, and being confirmed as eligible for study participation, patients will be randomized in a 1:1:1:1 ratio to receive placebo, BGB-DXP593 5 mg/kg, BGB-DXP593 15 mg/kg, or BGB-DXP593 30 mg/kg. Patient randomization will be stratified by country and disease severity (mild versus moderate COVID-19). The patients will receive a single intravenous infusion of placebo or BGB-DXP593 over 30 to 90 minutes. The patients will then be followed to Day 113 (± 7 days) to assess the efficacy, safety, PK, and immunogenicity. Nasopharyngeal swabs will be collected according to the Schedule of Assessments (Appendix 1) for RT-qPCR testing of SARS-CoV-2 to assess the change in viral load after study treatment. Approximately 172 patients will be randomized.

An Independent Data Monitoring Committee (IDMC) will periodically monitor safety and efficacy data. The first safety review is planned after at least 12 patients have been treated and followed up for 7 days.

The study schema is provided in Figure 2.

Figure 2: Study Schema

Note: Patients will be randomized based on stratification factors of country and disease severity (mild versus moderate COVID-19).

Patients will be monitored for safety, efficacy, PK, and immunogenicity during the study.

Assessments of safety will include AEs, SAEs, clinical laboratory tests, physical examinations, vital signs, and electrocardiograms (ECGs). AEs will be graded for severity according to the current version of the National Cancer Institute-Common Terminology Criteria for Adverse Events (NCI-CTCAE) Version 5.0. Refer to Section 9 for additional and specific information regarding AE monitoring and reporting.

RT-qPCR analysis will be used to assess the SARS-CoV-2 viral load in different samples at various timepoints, including nasopharyngeal swabs, saliva, and blood. The viral load in nasopharyngeal swabs will be used for primary efficacy analysis.

WHO 8-point ordinal scale will be used for clinical status assessment.

PK and ADA sampling will be conducted at timepoints specified in [Appendix 2](#).

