If at least one model is statistically significant, then we will reject the null hypothesis of a flat dose response relationship over viral shedding change at Day 8, with a multiple contrast test controlled for the family-wise type I error rate at one-sided $\alpha = 5\%$.

After rejecting the null hypothesis, the statistically significant model(s) from the above candidate set are selected as reference models. The dose-response relationship is estimated using model average technique to generate the new estimates.

The target dose(s) can be estimated from the average model by incorporating information on the minimum clinically relevant effect and by accounting for safety.

Comparisons of active doses to placebo (90% confidence intervals [CIs] and p-values) based on the mixed effects model will be reported. These are supportive analyses of the primary endpoint to supplement the MCPMod analysis, which is the primary analysis.

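### The stated power of at least 82% is not a minimum: under the plan's own inputs, power runs from about 70% to 82% across the five candidate dose-response shapes

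*Protocol*

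**What the plan says.** Protocol section 10.7 gives one power statement: "Forty-one patients are needed with primary endpoint data per arm to provide at least 82% power to detect non-flat dose-response relationship". SAP section 5 has the same sentence. The Synopsis, under Sample Size Calculation, says that 41 per arm are needed "to provide at least 82% power to detect non-flat dose-response relationship at one-sided significance level" of 5%.

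The listed assumptions are a normally distributed endpoint, one-sided alpha of 5%, "True maximum treatment effect size of BGB-DXP593 versus placebo is $-1.5 \log_{10}$ copies per mL", "Standard deviation is $3.2 \log_{10}$ copies per mL", and the candidate models of section 10.2.1. Table 4 in that section gives five shapes: Emax with ED50 2.6, Emax with ED50 12.5, sigmoid Emax with ED50 10 and h = 4, quadratic with delta = -0.022, and linear. The same section specifies a multiple contrast test with family-wise control at one-sided 5%. On allocation, section 3.1 says "patients will be randomized in a 1:1:1:1 ratio to receive placebo, BGB-DXP593 5 mg/kg, BGB-DXP593 15 mg/kg, or BGB-DXP593 30 mg/kg".

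Neither document gives power by shape, or says whether 82% is the minimum, mean or maximum over the shapes.

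**The concern.** A power of at least 82%, with the whole candidate set named as its basis and no shape singled out, reads as a floor that holds whichever candidate is true. MCPMod power varies with the true shape even when the maximum effect is fixed, because shapes differ in how far they spread the four dose means apart. An unlabelled single figure could therefore be the floor, the average or the ceiling.

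This is the trial's only power statement. Protocol section 10.8 says that the results will inform whether to start Phase 3 and at which dose. If the true power is nearer 70%, a non-significant result is weaker evidence against a 1.5 log10 effect than the plan implies. The Synopsis also gives ethics committees and regulators a more favourable design than the one proposed.

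**Working it through.** **Inputs.** From Protocol 10.7: n = 41 per arm, SD = 3.2, maximum effect 1.5 (sign reversed so that benefit is positive), one-sided alpha 5%. From section 3.1: equal allocation to 0, 5, 15 and 30 mg/kg. From Table 4: the five shapes.

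**Step 1: mean at each dose, scaled to a maximum of 1.5 over 0–30 mg/kg.**
- Emax: d/(ED50 + d). Sigmoid Emax: d⁴/(10⁴ + d⁴). Linear: d. Each is divided by its value at 30 and multiplied by 1.5.
- Quadratic: d − 0.022d². It peaks at 1/(2 × 0.022) = 22.7 mg/kg with height 11.36. At 30 mg/kg it is 30 − 19.8 = 10.2, giving 1.5 × 10.2/11.36 = 1.346.

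**Step 2: contrasts and noncentrality.** With equal arms, the optimal contrast for a shape is its mean vector, centred and scaled to unit length. On its own contrast the noncentrality is √(n × SS)/SD, where SS is the sum of squared deviations of the four means from their average. For linear the average is 0.625, so SS = 0.3906 + 0.1406 + 0.0156 + 0.7656 = 1.3125. The noncentrality is √(41 × 1.3125)/3.2 = 2.29.

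**Step 3: multiple contrast test.** The statistic is the largest of the five contrast t values, with 4 × 41 − 4 = 160 degrees of freedom. The one-sided 5% critical value, by simulation with 1.5 million draws, is 1.94. Power is the probability that the largest t exceeds it.

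| Shape | Means at 0, 5, 15, 30 | SS | Noncentrality | Power |
|---|---|---|---|---|
| Emax1 | 0, 1.072, 1.389, 1.5 | 1.41 | 2.37 | 71.9% |
| Emax2 | 0, 0.607, 1.159, 1.5 | 1.30 | 2.28 | 71.6% |
| sigEmax | 0, 0.089, 1.268, 1.5 | 1.82 | 2.70 | 82.2% |
| Quadratic | 0, 0.587, 1.327, 1.346 | 1.26 | 2.25 | 69.7% |
| Linear | 0, 0.25, 0.75, 1.5 | 1.31 | 2.29 | 69.8% |

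The minimum is 69.7%, the mean (71.9 + 71.6 + 82.2 + 69.7 + 69.8)/5 = 73.0%, and the maximum 82.2%. The plan's 82% is reproduced, but only as the maximum.

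**Step 4: a check that needs no simulation.** Suppose the true shape were known and only its own contrast tested, with no multiplicity correction (critical t = 1.654). From the noncentral t distribution, power would be 76.4%, 73.3%, 85.2%, 72.3% and 73.8%, in table order. Even this idealised test falls short of 82% for four of the five shapes.

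**Step 5: other readings.**

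| Reading | Minimum | Mean | Maximum |
|---|---|---|---|
| Quadratic scaled to 1.5 at a studied dose (quadratic alone rises to 77.8%) | 69.9% | 74.7% | 82.3% |
| 1.5 as the Emax asymptote | 46.8% | 66.7% | 81.4% |
| Variance treated as known | 70.4% | 73.7% | 82.8% |
| All 43 randomized per arm evaluable | 71.7% | 75.0% | 83.9% |
| Emax1 dropped from the set | 69.7% | 74.0% | 83.5% |
| Emax2 dropped from the set | 69.7% | 73.4% | 82.3% |

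**Step 6: what an 82% minimum would take.** With 57 evaluable per arm the minimum is 81.9%, and with 58 it is 82.5%. At 41 per arm, an SD of 2.7 gives 82.3%, and a maximum effect of 1.8 gives 83.0%.

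**The case against.** Four points can fairly be made for the plan.

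- **The source of the 82% is not documented.** That it is the best-shape figure is inferred from the numerical match. An alpha slip is another candidate: at one-sided 10% the minimum is 81.0% and the median 82.5%. This stands as a caution about the cause. It does not help the claim, because both documents state 5%.
- **The primary model adjusts for covariates.** The MMRM includes baseline viral shedding and severity, so the residual SD could be below 3.2 and actual power above 70%. Getting from 3.2 to 2.7 requires covariates to explain 1 − (2.7/3.2)² = 29% of the variance. That is possible, but neither document claims any such reduction, and the stated calculation uses 3.2.
- **82% is not a ceiling for every conceivable curve.** A step between 5 and 15 mg/kg (0, 0, 1.5, 1.5) has noncentrality 2.98 on the sigEmax contrast, above sigEmax's own 2.70, and so has higher power. This is correct: 82% is the maximum only within the prespecified set. Replacing "at least" with "at most" would therefore also be wrong unless limited to the candidate models.
- **The Phase 3 decision need not rest on significance alone.** Pairwise comparisons with 90% confidence intervals and a target-dose estimate will also be available. This softens the consequence but leaves the power statement wrong.

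Figure 3, which plots the shapes, was not available for this check. Table 4 and the 1.5 maximum fix the linear shape without it, and linear alone gives 70%.

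**Conclusion.** The power statement is wrong as written. Under the plan's own assumptions the minimum power over the five candidates is about 70%, 12 points below the stated figure, and only sigEmax reaches 82%. For the other four shapes the type II error is 28% to 30%.

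The result rests on optimal contrasts for equal arms, the usual quadratic parameterization (d + delta × d²), 41 evaluable patients per arm and SD 3.2. The minimum stays near 70% however the quadratic is scaled. The mean is less firm: 73.0% if the quadratic peaks at 1.5 between studied doses, and 74.7% if it reaches 1.5 at a studied dose. How the sponsor arrived at 82% is not established and does not affect the conclusion.

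**What to change.** In the Synopsis, Protocol section 10.7 and SAP section 5, replace the single figure with power by model. For example: with 41 evaluable patients per arm, power is about 70% (quadratic, linear), 72% (Emax1, Emax2) and 82% (sigEmax), with a mean of about 73% across the candidate models. State that the quadratic is scaled to peak at 1.5 within the dose range, or give the 74.7% mean if it is scaled to a studied dose.

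The sponsor should first re-run its R calculation and confirm the alpha, the scaling and which summary over shapes was reported. If a smaller residual SD from covariate adjustment was intended, that SD and its justification should be stated.

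The cost is wording only: no change to sample size, test or alpha, although the stated power becomes less favourable. If an 82% minimum was a real design requirement, the sample size has to be reopened, at about 58 evaluable patients per arm under the present assumptions.

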10.8. Interim Analyses

A primary analysis is planned after all patients have finished Day 8 visit or discontinued the study earlier. A decision will be made based on the interim results about whether a Phase 3 study should be initiated and which dose to be used for the Phase 3 study.

10.9. Missing Data Handling and Censoring Rules

In general, values for missing data will not be imputed, unless methods for handling missing data are specified.

For MMRM analysis, no imputation will be performed for missing viral shedding. If a patient misses a visit, the missing data will not be imputed. The mixed effect model will handle missing data based on a likelihood method under the "missing at random" assumption.

Sensitivity analyses using method of last observation carry forward (LOCF) may be considered to assess the potential impact from missing data, which will be detailed in the statistical analysis plan (SAP).

Missing dates or partially missing dates will be imputed conservatively for adverse events and prior/concomitant medications/procedures. Specific rules for handling of missing or partially missing dates for adverse events and prior/concomitant medications/procedures will be provided in the statistical analysis plan (SAP).

Censoring rules for analyses of time-to-event endpoints are determined as in Table 5.

Table 5: Censoring Rules for Analysis of Time-to-event Endpoints

No.	Situation	Date of Event or Censoring	Outcome
1	Target event documented	Date of occurrence of target event	Event
2	Multiple target events documented	Date of first occurrence of target event	Event
3	No target event or death occurred by the time of the End-of-Study Visit or the Safety Follow-up Visit (whichever is later), or data cut-off, or withdrawal from study, whichever comes first	Date of last adequate event assessment prior to or on the date of the End-of-Study Visit or the Safety Follow-up Visit (whichever is later), or data cut-off, or withdrawal from study, whichever comes first	Censored
4	Death and no target event prior to death	Date of data cutoff	Censored

